9 PLANNED STATISTICAL METHODS

9.1 General Considerations

A detailed statistical analysis plan will be developed separately and finalized prior to randomization of the first participant. Deviations from the protocol-planned analyses will be noted.

The statistical analysis of the data obtained from this study will be performed using SAS® Version 9.4 or higher. All statistical tests will be performed at the 0.05 (two-sided) significance level, unless otherwise noted.

The data collected in this study will be documented using summary tables and participant data listings. Continuous variables will be summarized using descriptive statistics, specifically the number of observations, mean, median, standard deviation, minimum and maximum. Categorical variables will be summarized by frequencies and percentages. The analysis of both efficacy and safety parameters will be conducted for each treatment group separately. Active treatment will be compared against placebo.

Baseline characteristics will be summarized using descriptive statistics or frequencies and percentages, as appropriate. No statistical hypothesis tests will be performed on these characteristics.

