9.2 Determination of Sample Size

For an annualized infection rate of 3% in the placebo arm (daily incidence = 0.000075), and assuming a true hazard ratio of 0.15 implying protective effect of NONS equivalent to a vaccine efficacy of 85%, a sample size of 11,480 participants randomized 1:1 (NONS:Placebo) and available in the modified intent-to-treat (mITT) population will provide 90% power to demonstrate superiority of NONS to placebo in preventing COVID-19 infections reported through 28 days, based on Cox regression model and a 2-sided 0.05-level test (Schoenfeld 1983). The expected number of events in the two arms is 2 and 10 for the NONS and placebo groups respectively. This further assumes 25% censoring during the 28-day period (1.05% loss per day).

Sample size calculations conducted under version 1.0 of the protocol (dated April 27, 2021) used estimates of annualized case rates as listed in Table 2. At that time, the recent estimated annualized infection rate based on confirmed cases ranged from 2.2 through 3.9% in select Canadian provinces, though there was considerable variability, and these rates underestimate the true infection rates considering those untested. The US and other nations may have substantially higher infection rates and require fewer subjects to be randomized.

In particular, for the Czech Republic, Slovakia, and Sri Lanka, the reported annualized rates are between 0.14% and 8.23%, 0.07% and 7.27%, and 1.48% and 6.18% respectively over the period of May 1, 2021, to July 31, 2021. We are therefore likely to have sufficient power to conduct this study in those countries.

The maximum number of participants who will be randomized is 13,000, in order to achieve a maximum of 11,480 participants initiating their randomized treatment assignment and entering the mITT population. If the infection rate is higher than assumed here, enrollment and randomization will be closed if the total number of COVID-19 events in the mITT population exceeds 18 cases, 50% more than the number expected for 90% power. This inflation accounts for the increased infection rate and the consequent increased risk of infection between the time of randomization and time of initiation of study treatment due shipping times.

Table 2 Daily COVID-19 Counts

Population	Estimated annualized rate in February 2021	Equivalent date based on study in control arm	assumption	Days Daily Confirmed case counts exceeded 3% / 4% annualized rate		

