9.5 Analysis of Efficacy

9.5.1 Primary Efficacy Analysis

The primary efficacy objective is to demonstrate that NONS product reduces the risk of COVID-19 infection. The associated null hypothesis is that the hazard ratio (HR) of NONS relative to placebo is greater than 1, or H_0 : $HR \ge 1$, or equivalently in terms of a vaccine efficacy, H_0 : $VE \ge 0$ where vaccine efficacy is calculated as VE = 100% x (1-HR). The HR will be estimated using a Cox proportional hazard regression model with a fixed effect only for treatment arm. Due to the small, expected event rate (see the Section 9.2), incorporation of additional fixed effects may not be possible. However, as a sensitivity analysis, a stratified Cox model using randomization strata (≥ 65 , <65 at increased risk, < not at increased risk) will also be fit. Similarly, age-group (\ge /<65) and region-specific models will be fit, aggregating adjacent provinces, states, or larger geographies to enable model convergence and evaluate, to the extent possible, whether differences exist.

The primary analysis will be executed in the mITT data set and count all cases occurring starting from the day after participants begin administering study treatment.

For all models, a 2-sided score-based 95% confidence interval (CI) and 2-sided p-value for the effect of NONS will be calculated.

The estimand of the primary analysis is a treatment policy strategy and will consider intercurrent events as censored. Specifically, participants who stop administering NONS for any reason, stop submitting data to the electronic patient-reported outcomes (ePRO) system, do not submit paper diaries, or are unreachable by telephone contact, will be censored on the day of their last ePRO clinical status submission or last available documented day on paper diary (ie, the last day confirming no positive COVID-19 test). Participants who submit COVID-19 test results following Day 28, will be censored at Day 28. Participants submitting a COVID-19 test result on or prior to Day 28 will be considered to have reached the primary endpoint on the day that the specimen (ie, nasal swab) is collected, not the date of the test. Positive test results obtained within 48 hours of randomization will be considered infected at randomization and not counted as events.

The Cox model will be fit to the following sets (if different) as sensitivity analyses:

- mITT set counting all cases after randomization,
- PP set counting cases after first administration,

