- PP set counting all cases after randomization, and
- Randomized set counting all cases after randomization

The primary analysis will be repeated in the following subgroups:

- Subjects unvaccinated against SARS-CoV-2 prior to randomization
- Subjects partially vaccinated against SARS-CoV-2 prior to randomization
- Subjects fully vaccinated against SARS-CoV-2 prior to randomization
- Subjects who are fully vaccinated and have received a booster shot against SARS-CoV-2 prior to randomization
- Subjects who become partially vaccinated against SARS-CoV-2 during the course of the study
- Subjects who become fully vaccinated against SARS-CoV-2 during the course of the study
- Subjects who receive a booster vaccine against SARS-CoV-2 during the course of the study

Specific procedures to account for missing data, unused or spurious data and criteria for termination will be delineated in the SAP. Procedures for reporting any deviation(s) from the original statistical plan will be described in the SAP and justified (if needed) in the final clinical study report.

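### Section 9.5.1 sets out to see whether the effect differs by age and region, but offers only a separate p-value within each group and no test of heterogeneity

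*Combined protocol and SAP*

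**What the plan says.** Section 9.5.1 makes the mITT Cox model with treatment as the only fixed effect the primary analysis. A Cox model stratified by the randomization strata is a sensitivity analysis. The section then plans models specific to age group (65 or over, under 65) and to region, merging adjacent geographies "to enable model convergence and evaluate, to the extent possible, whether differences exist". The output is the same throughout: "For all models, a 2-sided score-based 95% confidence interval (CI) and 2-sided p-value for the effect of NONS will be calculated".

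On vaccination the section says: "The primary analysis will be repeated in the following subgroups". Seven groups follow. Four are defined before randomization: unvaccinated, partially vaccinated, fully vaccinated, and fully vaccinated with a booster. Three are defined by a vaccine dose received during the study.

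Section 9.1 sets the level: "All statistical tests will be performed at the 0.05 (two-sided) significance level, unless otherwise noted". Section 9.5.1 notes nothing different for subgroups. It gives no interaction or heterogeneity test, no multiplicity rule, no minimum number of events, and no statement that subgroup results are descriptive. It concedes that further fixed effects may not be possible with so few events.

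**The concern.** The stated aim for age and region is to learn whether the effect differs, but the tool supplied tests something else. A p-value within a group asks whether that group's hazard ratio is 1. Two such p-values, one below 0.05 and one above, say nothing reliable about whether the two hazard ratios differ. With a dozen events, the group with more cases will tend to be significant and the other not, even when the effect is identical.

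Three further features add to this:
- As worded, a participant with a booster also meets the definition of fully vaccinated, so those two groups overlap.
- Three vaccination groups are formed by what happens after randomization, so within them the arms are no longer protected by randomization.
- Regions are merged according to whether a model converges, which depends on where the events fall and in which arm.

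At stake is how subgroup tables are read. A uniform effect could look confined to one group, or a null trial could appear to contain a group in which the spray works.

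**Working it through.** **1. The plan's own figures.** Section 9.2 gives HR 0.15, two-sided 0.05, 90% power, 11,480 participants at 1:1, daily placebo incidence 0.000075, and 25% censoring over 28 days.
- Events needed (Schoenfeld): 4 × (1.960 + 1.282)² / (ln 0.15)² = 11.68, so 12.
- Censoring hazard: −ln(0.75)/28 = 0.01027 per day. Mean days at risk: (1 − 0.75)/0.01027 = 24.3.
- Placebo events: 5,740 × 0.000075 × 24.3 = 10.5. NONS events: 0.15 × 10.5 = 1.6. Total about 12, matching the stated 10 and 2.

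Enrollment closes once events exceed 18, so 12 and 18 are used below.

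**2. What a small group can show.** With 1:1 allocation and rare events, the score statistic for p placebo and q NONS cases is approximately z = (p − q)/√(p + q).
- 3 v 0: z = 1.73, p = 0.083. With 3 or fewer events, p<0.05 is impossible.
- 4 v 0: z = 2.00, p = 0.046. Under no effect, a 4-event group splits 4:0 one way or the other with probability 2 × 0.5⁴ = 12.5%.
- At HR 0.15 each case falls in the placebo arm with probability 1/1.15 = 0.870. Power within a group is 0.870⁴ = 57% at 4 events, 0.870⁶ = 43% at 6 (only 6:0 is significant), and 67% at 9 (9:0 or 8:1).

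**3. Same effect in both age groups.** Simulation with HR 0.15 in each group and Poisson event totals, among trials with a significant primary result. The share aged 65 or over is an assumption.

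| Share aged 65 or over | Expected events in that group (12 / 18) | Exactly one age group significant, 12 events | Same, 18 events |
|---|---|---|---|
| 10% | 1.2 / 1.8 | 90% | 91% |
| 20% | 2.4 / 3.6 | 78% | 71% |
| 30% | 3.6 / 5.4 | 67% | 58% |
| 50% | 6 / 9 | 59% | 49% |

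At 12 events, discordance with at least 4 events in both groups makes up only 2, 13 and 27 percentage points for shares of 10, 20 and 30%. The remaining 90 − 2 = 88, 78 − 13 = 65 and 67 − 27 = 40 points come from trials in which a group has fewer than 4 events. With a 50/50 split, low power within each group plays the larger part.

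**4. No effect anywhere.** Age, region and the four baseline vaccination groups are simulated as independent factors, with the vaccination groups treated as exclusive. The chance of at least one subgroup p<0.05 by the score test is:
- 8-28% at 12 events and 9-35% at 18, across the assumed shares;
- 8-10% when one stratum dominates every factor (85-95% of participants), and 22-35% when the splits are balanced;
- for hits favouring NONS, about half: 4-14% at 12 events and 5-18% at 18;
- 3-9% if exact p-values replace score p-values.

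**5. One heterogeneity test per factor instead.** With a uniform HR of 0.15, a score test of treatment by factor declares a false difference in about 2-5% of trials per factor, and in about 9-11% for any of three unadjusted factors (about 13% when HR is 1). Its power for HR 0.15 in one of two groups and 1.0 in the other is about 28% at 12 events and 39-41% at 18. A Fisher exact test has 11-28%.

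**The case against.** The plan names one primary analysis and attaches no success rule or claim to any subgroup. It hedges the aim with a qualifier and admits that the data are thin. A reader might infer that the plan will conclude that the spray works in one group and not in another. The documents do not say so: the simulations show discordant or chance significance, not a conclusion that anyone has committed to drawing. That part of the objection stands.

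A reader might also infer that the vaccination groups are to be compared with one another. The aim of finding differences is written for age and region only. For vaccination the plan simply repeats the primary analysis, although each repeat still carries a p-value.

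A single figure such as a quarter of null trials would be tempting too. It holds only for fairly even group shares. Many of those hits are 4:0 or 5:0 splits, for which the Cox hazard ratio does not converge, and the plan would merge regions in that situation. Likewise, much of the discordance by age at 12 events comes from groups too small to be significant, some with no events at all. These points limit the size of the problem, but they also show why such p-values carry little information.

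Section 9.1 defers detail to a separate SAP, which could add a heterogeneity test. The text reviewed contains none. Section 9.5.1 defers missing data, unused or spurious data, and termination criteria to the SAP, but not this. Finally, any heterogeneity test here has low power. That is true, and is a reason to rely on estimates rather than on separate p-values.

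**Conclusion.** The point holds as a mismatch between aim and method. Section 9.5.1 asks whether effects differ by age and region but supplies only within-group p-values, which cannot answer that. Discordant significance between the two age groups under a uniform HR of 0.15 is common: about 67-90% of positive trials at 12 events and 58-91% at 18 if 10-30% are aged 65 or over. It is not universal, since an even split at 18 events brings it to about 49%. The null figure is a range of roughly 8-35%, about half of it favouring NONS. Every one of these rates rests on assumed group shares, and the null figures also on an assumed number of regions, because the protocol gives neither. The overlap of two baseline vaccination groups and the post-randomization definition of three others follow from the text and need no assumption. The primary endpoint's alpha, power and estimate are unaffected. The change is worth making before unblinding, but it concerns interpretation of subgroups only.

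**What to change.** Amend section 9.5.1, and carry the same text into the SAP:
- (a) For each subgroup report cases, person-days, HR or VE and a 95% CI, labelled descriptive, with no subgroup p-values and no subgroup claims.
- (b) Assess differences by one heterogeneity test per baseline factor (age, region, baseline vaccination): either an exact test of arm by subgroup among the cases, which needs no extra Cox term, or a treatment-by-factor score test. State that its power is low and that a non-significant result does not show a uniform effect.
- (c) Make the four baseline vaccination groups mutually exclusive.
- (d) Fix the region groupings before unblinding, without using events by arm.
- (e) Treat the three during-study vaccination groups as descriptive only. A heterogeneity test does not cure their being defined after randomization.

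The cost is a few lines of text, minor programming and the loss of nominal subgroup p-values. Three unadjusted heterogeneity tests still carry some chance of a false difference, so they too should be read as exploratory.

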7.12.1 Removal of Participants from the Trial or Study Treatment

The Investigator may withdraw a participant from the study for any of the following reasons:

- A protocol violation occurs,
- A serious or intolerable adverse event occurs,
- A clinically significant change in a laboratory parameter occurs,
- The Sponsor or Investigator terminates the study, or
- The participant requests to be discontinued from the study.

A participant may choose to discontinue study treatment and/or withdraw from the study at any time. Participants who become pregnant during the study are to be withdrawn from study treatment. In the absence of a medical contraindication, every effort should be made by the Investigator to encourage participants who prematurely discontinue treatment to remain in the study as appropriate and, at a minimum, follow the participant for safety data collection.

7.12.1.1 **Discontinuation from Study Drug Treatment**

Participants may discontinue for the following reasons: any study drug related AEs that in the opinion of the Investigator, makes it unsafe for the participant to continue; any study drug related AE that repeats upon re-challenge.

A participant may be discontinued prematurely from study drug treatment for the following reasons:

- AE (including hospitalization for COVID-19/sequalae)
- Withdrawal by participant (specify reason in the eCRF)
- Lost to Follow-up
- Pregnancy

- Physician decision (ie, Investigator decision specify reason in the eCRF)
- Sponsor decision (specify reason in the eCRF)
- Noncompliance with study protocol
- Other (specify reason in the eCRF)

7.12.1.2 **Discontinuation from Study**

A participant may be discontinued prematurely from the study (in its entirety) for the following reasons:

- AE (including hospitalization for COVID-19/sequalae)
- Withdrawal by participant (specify reason in the eCRF)
- Lost to Follow-up
- Death
- Physician decision (ie, Investigator decision specify reason in the eCRF)
- Sponsor decision (specify reason in the eCRF)
- Noncompliance with study protocol
- Other (specify reason in the eCRF)

If a participant is withdrawn because of an adverse experience, the participant will be followed and treated by their health care provider (with documented follow-up) until the abnormal parameter or symptom has resolved or stabilized.

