9.3 Analysis Populations

Analysis populations are Randomized participant, mITT, Per-Protocol (PP), and the Safety population (all participants receiving any dose of treatment), the Per Protocol population (received drug and had no major documented protocol violations), defined as in

Table 3.

Table 3 Populations for Analysis

Population	Description
Randomized	All participants randomized regardless of adherence to treatment or study status, analyzed as randomized.
mITT	All participants in the Randomized population who received at least one dose of the test article (NONS or placebo), analyzed as randomized.
Daily Use	All participants in the mITT set who documented at least one self-administered NONS dose per day on at least 25 of 28 expected dosing days or 90% of days while on study treatment. Analyzed as treated
Per Protocol	All participants in the mITT set who documented self-administered NONS on at least 25 of 28 expected dosing days or 90% of days and 80% of expected doses while on study treatment. Analyzed as treated.
Safety	All randomized participants who receive at least 1 dose of the study intervention.

Abbreviations: mITT=modified intent-to-treat; NONS=nitric oxide nasal spray.

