13 APPENDICES

Appendix 1 Schedule of Events

Table 4 Schedule of Events

	Screening a Baseline	Daily on TX	Early TX Day	Last Tx Day	Post-Tx Follow-up		
Assessments			Phone Assessment 1	Phone Assessment 2	Phone Assessment 3	ET	
Visit Type (per specific country regulatory legislation)	Remotely or On-Site	Remotely	Remotely	Remotely	Remotely or On-Site	Remotely or On-Site	
Study Day	-7 to 1	1-35 ^d	7+3	28 +2	End of Study 35±3		
Participant Informed Consent (Virtual, if applicable/respective country) b	X						
Demographics (Virtual, if applicable/respective country)	X						
Medical History (Virtual, if applicable/respective country)	X						
Clinical Exam including Vitals (Virtual, if applicable/respective country)	X				X	X	
Pregnancy Test (Urine) ^c	X				X	X	
Concomitant Medications ^d	X	X	X	X	X	X	
Randomization	X						
Study treatment instructions ^e	X		X				
COVID related symptom assessment ^f			X	X	X	X	
NONS Self Administration ^g		X	X	X			
Questionnaire (online/paper) h		Xi	X	X	X	X	
Adverse Events		X	X	X	X	X	
Study Drug Accountability/Compliance		X	X	X		X	
Report if tested positive for COVID-19 infection		X	X	X	X	X	
Report need for Hospitalization/ER Visit for COVID-19 related sequelae		X	X	X	X	X	

Abbreviations: ER=emergency room; ET= early termination; NONS= nitric oxide nasal spray; Tx=treatment.

NONS (nitric oxide nasal spray)
Clinical Trial Protocol: COVID-NONS-04

- ^a Screening and baseline are to be taken within 7 days but may be taken at the same assessment. Post-Treatment Follow-up visits (end of study and ET) may be performed remotely. For countries requiring an in-person visit, these will be performed on-site, unless the participant is hospitalized, in quarantine or unable to visit the site for any reasonable cause as per the investigators' judgement; these visits may then be performed remotely and will not be considered a protocol deviation. Follow-up of all adverse events must be completed as described in the protocol Section 7.
- Participants will be asked to designate an emergency contact who will also sign informed consent. In the event the participant is hospitalized and cannot complete their treatment diary or questionnaire emergency contacts will be encouraged to provide symptoms on behalf of a participant in a COVID-19 symptoms list Diary (Appendix 2).

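### The primary estimand is called treatment policy, yet stopping the spray is a censoring reason, so an infection after stopping could be coded as an event or as censored

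*Combined protocol and SAP*

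**What the plan says.** Section 9.5.1 (Primary Efficacy Analysis), repeated in the Synopsis, reads: "The estimand of the primary analysis is a treatment policy strategy and will consider intercurrent events as censored". The next sentence in 9.5.1 lists who is censored. It begins with "participants who stop administering NONS for any reason, stop submitting data to the electronic patient-reported outcomes (ePRO) system", adds people who return no paper diary or cannot be reached by telephone, and says that they "will be censored on the day of their last ePRO clinical status submission or last available documented day on paper diary".

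Two other sentences in 9.5.1 carry no on-treatment condition. The mITT analysis is to "count all cases occurring starting from the day after participants begin administering study treatment". The Day 28 rule says "Participants submitting a COVID-19 test result on or prior to Day 28 will be considered to have reached the primary endpoint", dated at specimen collection.

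Three further places bear on the point:

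- Section 9.3, Table 3 defines the Randomized set as "All participants randomized regardless of adherence to treatment or study status, analyzed as randomized".
- Appendix 1, Table 4 has a row "Report if tested positive for COVID-19 infection", marked for the daily record (Days 1-35), the phone contacts and early termination.
- Section 7.12.1 asks investigators to encourage people who stop treatment to stay in the study and, "at a minimum, follow the participant for safety data collection".

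**The concern.** Stopping the spray is an intercurrent event, not a loss of information. Someone who stops on Day 10 can still report a positive swab on Day 18, and Table 4 provides the means to record it. The censoring list treats that person like someone who cannot be reached. The estimand label and the Day 28 sentence point the other way.

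Two things are at stake. The first is reproducibility: two analysts following 9.5.1 could code the same infection differently, in a trial whose result rests on about 12 events. The second is validity: if stopping is related to early infection (for example, people stop when symptoms begin) and the pattern differs by arm, censoring stoppers is informative and shifts the hazard ratio.

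**Working it through.** **Reading the text.** Consider a participant who stops on Day 10, keeps reporting, and has a positive swab on Day 18.

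| Rule in 9.5.1 | Coding of the Day 18 swab |
|---|---|
| Treatment-policy label | Event |
| Intercurrent events censored; stopping listed as a trigger | Censored |
| Censoring date = last status day | Either: reporting may keep the person at risk, or censoring falls on the last negative status day before the swab |
| Day 28 sentence | Event on Day 18 |

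No sentence ranks these rules. The listed sensitivity analyses change the population (PP, Randomized) or the start of counting. None states that the stopping rule is lifted.

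**The plan's own figures (Section 9.2).** Inputs: 5,740 per arm, placebo hazard h = 0.000075 per day, HR 0.15, loss L = 0.0105 per day, 28 days.

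- Expected events per arm = 5,740 × h/(h+L) × (1 − exp(−28(h+L))). Placebo: 10.43. NONS, with 0.15h: 1.57. Total: 12.0, against the stated 10 and 2.
- Schoenfeld events for 90% power = 4(1.96 + 1.28)²/(ln 0.15)² = 11.7, rounded up to 12. Power at 12 events is 91%.
- With no loss, the placebo arm would have 12.04 events, so the planned censoring removes 12.04 − 10.43 = 1.61.

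The design figures reproduce.

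**How far one coding decision can move the result.** Approximate score statistic z = (x0 − x1)/√(x0 + x1), with x0 placebo and x1 NONS events.

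| Placebo v NONS | z | two-sided p |
|---|---|---|
| 10 v 2 | 8/√12 = 2.31 | 0.021 |
| 10 v 3 | 7/√13 = 1.94 | 0.052 |
| 11 v 3 | 8/√14 = 2.14 | 0.033 |

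An exact binomial test on the split gives p = 0.039 for 10 v 2 and 0.092 for 10 v 3.

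**Possible bias if post-stop positives are not counted.** The loss shares below are assumed, because the documents give none. True HR is 1 and each arm expects 10.43 infections. With q1 and q0 the shares of NONS and placebo infections lost, apparent HR = (1 − q1)/(1 − q0). The false-benefit rate is the probability that z > 1.96 when the counts are Poisson with means 10.43(1 − q0) and 10.43(1 − q1).

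| NONS lost | Placebo lost | Apparent HR | False-benefit rate |
|---|---|---|---|
| 0% | 0% | 1.00 | 2.6% |
| 15% | 10% | 0.94 | 3.3% |
| 20% | 10% | 0.89 | 4.3% |
| 30% | 10% | 0.78 | 7.2% |
| 50% | 10% | 0.56 | 18% |

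**Effect on power of counting post-stop infections.** Suppose a share f of the planned censoring is stoppers who can still be followed, and protection ends at once on stopping. Each arm then gains f × 1.61 events. The Poisson column enumerates Poisson counts against the approximate score test.

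| f | Placebo v NONS | HR | Power, Poisson | Power, Schoenfeld |
|---|---|---|---|---|
| 0 (plan) | 10.43 v 1.57 | 0.15 | 77% | 91% |
| 0.25 | 10.83 v 1.97 | 0.18 | 73% | 86% |
| 0.5 | 11.24 v 2.37 | 0.21 | 70% | 82% |
| 1 | 12.04 v 3.17 | 0.26 | 64% | 74% |

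If protection persists fully after stopping, HR stays at 0.15 and Schoenfeld power rises to between 92% and 94%.

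**The case against.** The strongest reply is that the censoring date is the last status day and not the day the spray stops. A stopper who reports daily would then stay at risk to Day 28, later positives would count, and nothing would be lost. That reading is available, but it makes stopping redundant as a censoring trigger, and the plan's gloss on the date, as the last day confirming no positive test, equally allows censoring just before the positive. What stands is that the bias table applies under one of two readings.

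The Day 28 sentence can also be read mainly as a dating rule. Even so, nothing else decides the case.

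The 10 v 3 example adds an event to one arm only. Lifting the rule could add one to each arm, and 11 v 3 stays below 0.05 on the score test. That is fair: the example shows what one infection can do, not what is expected.

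Section 7.12.1 does encourage stoppers to remain in the study. Its stated minimum is safety data, though, so infection reporting after stopping is hoped for and not required.

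Finally, Section 9.5.1 leaves missing-data procedures to a SAP, and the Randomized set ignores adherence. A positive swab after stopping is observed data, not missing data, and Table 3 defines who is in the set, not which of their infections count.

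**Conclusion.** The concern holds, and it should be fixed before any data are analysed. The estimand label and the censoring rule contradict each other, and the primary event is undefined for infections after stopping. This follows from the text alone. With about 12 expected events, one such infection in the NONS arm would move 10 v 2 across the 0.05 line on both the score and the exact test.

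The bias is conditional. It requires that post-stop positives go uncounted and that the share of infections lost differs by arm. Under the assumed losses, small differences matter little (3.3% false benefit against 2.6%) and large ones matter a great deal (18%). The case for change rests on the undefined event rule, not on proven bias.

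**What to change.** In Section 9.5.1, the Synopsis and the SAP:

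- Count every otherwise eligible positive specimen through Day 28 in both arms, whether or not the spray is still used. Keep the 48-hour exclusion and the start of counting on the day after first dose.
- Censor only at loss of contact, end of reporting or withdrawal of consent, at the last known status date.
- Name study treatment in place of NONS in the rule, so that it plainly covers both arms.
- State in Section 7.12.1 and Table 4 that infection-status reporting continues to Day 28 after stopping.
- Keep censoring at stopping as a named on-treatment sensitivity analysis.

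The cost is wording plus a firm reporting requirement that uses contacts already scheduled. The statistical cost is possible dilution, as in the power table above, so the power statement in Section 9.2 should be rechecked under the chosen rule. Relabelling the estimand alone would remove the contradiction in words but leave the risk of informative censoring in the primary analysis.
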